4.3. Randomization Criteria

Subjects will be randomized into the study provided they have satisfied all subject selection criteria.

4.4. Lifestyle Guidelines

The following guidelines are provided:

4.4.1. Meals and Dietary Restrictions

- Subjects must abstain from all food and drink (except water) at least 10 hours prior to any fasting laboratory evaluations. Water may be consumed without restriction. Non-caffeinated drinks may be consumed with meals and the evening snack.
- Breakfast will be provided in the morning during in-patient confinement periods. On days when MMTT is being performed, the liquid meal for the MMTT will substitute for breakfast and will be provided after an overnight fast of at least 10 hours.
- Lunch will be provided approximately 4 hours after dosing (and after completion of MMTT on days in which this procedure occurs), or approximately 12 noon on non-dosing days.

- Dinner will be provided approximately 9 to 10 hours after dosing, or approximately 6 pm on non-dosing days.
- An evening snack may be permitted approximately 13 to 15 hours after dosing, or approximately 10 PM on non-dosing days.
- While confined, the total daily nutritional composition should be approximately 50% carbohydrate, 35% fat and 15% protein. A BMI adjusted diet is also acceptable. The daily caloric intake per subject should be adequate to maintain current weight.
- The meals and snacks provided during confinement for mean daily glucose (MDG) will be standardized and should be approximately 50% carbohydrate, 35% fat and 15% protein. Within each subject, the same meals and snacks must be provided during every MDG profile. On days when mean daily glucose profiles are being collected meals will be given at approximately 08:00 AM, 12:00 PM and 6:00 PM. Subjects will have 30 minutes to finish the meal and must consume the entire meal. Collection times are from the start of the meal.
- For 72 hours prior to each confinement, the subjects should be counseled to consume >150 g carbohydrates/day as an outpatient and provided when confined in the CRU.

4.4.2. Alcohol, Caffeine and Tobacco

- Subjects will abstain from alcohol for 24 hours prior to admission to the CRU (Clinical Research Unit) and during confinement in the research unit. Subjects will abstain from alcohol for 24 hours prior to all remaining study visits. Subjects may undergo an alcohol breath test at the discretion of the investigator.
- Subjects will abstain from caffeine-containing products for 24 hours prior to the start of dosing and 24 hours prior to all remaining study visits. Plus 4 hours after dosing on dosing days.
- Subjects will abstain from the use of tobacco- or nicotine-containing products for 24 hours prior to dosing, 24 hours after dosing and 24 hours prior to all remaining study visits.

4.4.3. Activity

- Subjects will abstain from strenuous exercise (eg, heavy lifting, weight training, calisthenics, aerobics) for at least 48 hours prior to each blood collection for clinical laboratory tests. Walking at a normal pace will be permitted.

4.4.3.1. Contraception

4.4.3.2. Women– Childbearing Potential

Only women of non-child bearing potential will be enrolled in this study. The criteria for defining women of non-child bearing potential is in [Section 4](#).

4.4.3.3. Men

All men who, in the opinion of the investigator, are biologically capable of having children and are sexually active, must agree to use a highly effective method of contraception consistently and correctly for the duration of the study and for at least 60 days after the last dose of investigational product. The investigator or his/her designee, in consultation with the subject, will confirm the subject has selected the most appropriate method of contraception for the individual subject and his partner from the permitted list of contraception methods (see below) and instruct the subject in its consistent and correct use. Subjects need to affirm that they meet at least one of the selected methods of contraception. The investigator or his/her designee will discuss with the subject the need to use highly effective contraception consistently and correctly according to the [Schedule of Activities](#) (SOA) and document such conversation in the subject's chart. In addition, the investigator or his/her designee will instruct the subject to call immediately if the selected contraception method is discontinued or if pregnancy is known or suspected.

Highly effective male contraception include: male condom WITH a spermicide (ie, foam, gel, film, cream or suppository) and male sterilization with the absence of sperm in the post-vasectomy ejaculate. In addition, males will not donate sperm during and 60 days post trial.

4.5. Sponsor Qualified Medical Personnel

The contact information for the sponsor's appropriately qualified medical personnel for the study is documented in the study contact list.

To facilitate access to appropriately qualified medical personnel on study related medical questions or problems, subjects are provided with a contact card. The contact card contains, at a minimum, protocol and investigational compound identifiers, subject study number, contact information for the investigational site and contact details for a help desk in the event that the investigational site staff cannot be reached to provide advice on a medical question or problem originating from another healthcare professional not involved in the subjects participation in the study. The help desk number can also be used by investigational staff if they are seeking advice on medical questions or problems, however it should only be used in the event that the established communication pathways between the investigational site and the study team are not available. It is therefore intended to augment, but not replace the established communication pathways between the investigational site and study team for advice on medical questions or problems that may arise during the study. The help desk number is not intended for use by the subject directly and if a subject calls that number they will be directed back to the investigational site.

5. STUDY TREATMENTS

5.1. Allocation to Treatment

The investigator's knowledge of the treatment should not influence the decision to enroll a particular subject or affect the order in which subjects are enrolled.

The investigator will assign subject numbers sequentially to the subjects as they are screened for the study. Pfizer will provide a randomization schedule to the investigator and, in accordance with the randomization numbers, the subject will receive the study treatment regimen assigned to the corresponding randomization number.

Eligible subjects will be randomly assigned through an Interactive Voice Response System (IVRS) to a study treatment cohort. Randomization numbers will be assigned by the IVRS. Subjects in the SAD portion will be randomized to receive a single-dose of either PF-06293620 SC 0.3 mg/kg to 6 mg/kg (Cohorts 1 through 4) or placebo, or PF-06293620 IV 1 mg/kg (Cohort 5) or placebo, in a 6:2 ratio PF-06293620:placebo in all cohorts. All subjects will receive PF-06293620 or placebo once in the study treatment period.

Subjects in the MAD portion will be randomized to receive multiple-doses of either PF-06293620 or placebo SC every 4 weeks in an 8:2 ratio PF-06293620:placebo. Based on the ongoing review of the safety data of the previous cohort(s) will be used to determine the dose and dose regimen of the fourth planned cohort.

5.2. Breaking the Blind

At the initiation of the study, the study site will be instructed on the method for breaking the blind. The method will be either a manual or electronic process. Blinding codes should only be broken in emergency situations for reasons of subject safety. Whenever possible, the investigator or sub-investigator should consult with a member of the study team prior to breaking the blind. When the blinding code is broken, the reason must be fully documented and entered on the case report form (CRF)/data collection tool (DCT).

Only the investigator site(s) and the study monitor(s) will be blinded to study treatment. Pfizer personnel will be unblinded to subject treatments in order to permit real-time interpretation of the safety and pharmacokinetic data; and provide information necessary to potentially alter the dose escalation sequence. The study monitor will remain blinded to treatment until all monitoring for the study has been completed. To minimize the potential for bias, treatment randomization information will be kept confidential by Pfizer personnel and will not be released to the investigator or investigator site personnel until the study database has been locked.

Blood specimens will be obtained from all subjects for pharmacokinetic analysis to maintain the study blind at the investigator site. Specimens from subjects randomized to placebo will not be routinely analyzed.

5.2.1. Drug Supplies

5.2.2. Formulation and Packaging

PF-06293620 will be provided as a solution for injection in a 20 mM histidine buffer at pH 5.8, at a concentration of 50 mg/mL. The drug product is supplied in 6 mL Type 1 clear glass vial sealed with a coated serum stopper and an aluminum seal, with a nominal fill volume of 4 mL

PF-06293620 will be shipped under refrigerated conditions (2-8°C) and should be stored under refrigerated conditions (2-8°C).

The placebo will be an appropriate sterile diluent solution supplied by the study site. The placebo formulation will be specified in the Dosage and Administration Instructions.

5.2.3. Preparation and Dispensing

PF-06293620 and placebo will be prepared according to the Dosage and Administration Instructions (DAI) that will be provided to the site. Drug will be prepared by qualified unblinded site personnel and administered by blinded staff in a blinded fashion to the subject. Following preparation for administration, PF-06293620 or placebo should be administered as soon as possible. The prepared solution may be stored at refrigerated conditions (2-8°C) or at room temperature (15-25°C) for a limited time until the time of administration, as specified in the DAI. Product should be prepared and used on the same day.

Details of dose preparation will be given under a separate cover (DAI).

Only qualified personnel who are familiar with procedures that minimize undue exposure to them and to the environment should undertake the preparation, handling, and safe disposal of chemotherapeutic agents.

5.2.4. Administration

Following an overnight fast of least 10 hours, subjects will receive study medication at approximately 0800 hours (plus or minus 2 hours). Qualified and trained investigator site personnel will administer study drug to subjects either by subcutaneous injection (SAD Cohort 1-4 and all MAD Cohorts) to the abdomen, or as a single IV infusion (SAD Cohort 5 only) by rate controlled intravenous infusion device over approximately 60 minutes. For subjects receiving two or more subcutaneous injections, study drug should be administered to two or more different quadrants of the abdomen; one or two injections per quadrant. Study staff should refer to the DAI for specific instructions on the handling and administration of study medication.

Subjects should take their metformin according to their usual time schedule and regimen. On Day 1 (all SAD and MAD cohorts), and on additional days where study drug is administered (MAD cohorts only) metformin should be taken prior to receiving study treatment.

Medication errors may result, in this study, from the administration or consumption of the wrong product, by the wrong subject, at the wrong time, or at the wrong dosage strength. Such medication errors occurring to a study participant are to be captured on the medication error case report form (CRF) which is a specific version of the adverse event (AE) page and on the SAE form when appropriate. In the event of medication dosing error, the sponsor should be notified immediately.

Medication errors are reportable irrespective of the presence of an associated AE/SAE, including:

- Medication errors involving subject exposure to the investigational product.
- Potential medication errors or uses outside of what is foreseen in the protocol that do or do not involve the participating subject.

Whether or not a medication error is accompanied by an AE, as determined by the investigator, the medication error is captured on the medication error version of the adverse event (AE) page and, if applicable, any associated adverse event(s) are captured on an adverse event (AE) CRF/DCT page.

5.2.5. Compliance

PF-06293620/placebo will be administered by appropriately trained site personnel in the clinic.

Subjects will self administer metformin during their participation in the study. On specific days (See [Schedule of Activities](#)), site personnel will ask subjects the number of doses taken since the last visit. The information will be recorded on the eCRF.

Subjects will be educated on the importance of taking their daily dosages of metformin during the study period.

5.3. Drug Storage and Drug Accountability

PF-06293620 active vials should be stored refrigerated at 2-8°C. Storage conditions stated in the SRSD (ie, *Investigator Brochure [IB]*, *Core Data Sheet [CDS]*, *United States Package Insert [USPI]*, *Summary of Product Characteristics [SPC]*, or *Local Product Document [LPD]*) will be superseded by the label storage.

Investigators and site staff are reminded to check temperatures daily (ie, manually or by using alarm system to alert of any excursions) on working days only, and to ensure that thermometers are working correctly as required for proper storage of investigational products. These include thermometers for both the room storage and refrigerator storage. Any temperature excursions should be addressed according to appropriate standard operating procedures.

The investigational product(s) must be stored as indicated. Deviations from the storage requirements, including any actions taken, must be documented and reported to the sponsor. Once a deviation is identified, the investigational product must be quarantined and not used until the sponsor provides documentation of permission to use the investigational product.

At the end of the study, Pfizer will provide instructions as to disposition of any unused investigational product. If Pfizer authorizes destruction at the study site, the investigator must ensure that the materials are destroyed in compliance with applicable environmental

regulations, institutional policy, and any special instructions provided by Pfizer. Destruction must be adequately documented.

5.4. Concomitant Medication(s)

Sporadic use of any homeopathics or nutritional supplements should be discouraged as they may confound interpretation of study treatment results. Subject may be on dietary supplement or herbal medicine as long as dose is stable within 2 weeks of screening and throughout the duration of the study.

All concomitant medications taken during the study must be recorded with indication, daily dose, and start and stop dates of administration. All subjects will be questioned about concomitant medication at each clinic visit.

Medications taken within 28 days before the first dose of study medication will be documented as a prior medication. Medications taken after the first dose of study medication will be documented as concomitant medications.

5.4.1. Permitted Medications

Subjects should remain on their dosage of metformin throughout the study. They are allowed to take metformin during the fasting period. As noted in [Section 5.4](#), the date, the time of dose and the dosage must be recorded.

Medications required for treatment of preexisting, stable medical conditions are permitted.

5.5. Rescue Therapy

Standard medical supportive care must be provided to manage AEs. For medical management of hypoglycemia (See [Section 7.6](#)), the investigator should obtain a blood sample for glucose first and then may administer oral carbohydrate, glucagon or IV glucose according to medical judgment.

For the MAD portion of the study, if a subject has sustained high fasting plasma glucose concentrations on two consecutive measurements (ie, measured on different days), based on the ranges below, the investigator should recommend further follow-up and treatment.

- Fasting Plasma Glucose >270 mg/dL (15 mmol/L) at Week 6.
- Fasting Plasma Glucose >240 mg/dL (13.3 mmol/L) at Week 12.
 - Reinforcement of an appropriate diet is encouraged.

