- l. Mean Daily Glucose Profile: blood sample for plasma glucose level will be collected: 30 minutes before and immediately prior to AM meal, 30, 60, 90, 120 and 180 minutes after the start of the AM meal; immediately prior to the midday meal, 60, 120 and 180 minutes after the start of the midday meal; immediately prior to the evening meal, 60, 120 and 180 minutes after the start of the evening meal; approximately at 11:00 PM; 0300 AM and 0730 (immediately prior to the AM meal). On days when mean daily glucose profiles are being collected meals will be given at approximately 08:00 AM, 12:00 PM and 6:00 PM. Subjects will have 30 minutes to finish the meal and must consume the entire meal. Collection times are from the start of the meal.
- m. 24 hour ambulatory blood pressure monitoring: blood pressure assessments will be initiated in the AM on scheduled days and will be initiated at approximately the same time for a subject throughout the duration of the study.
- n. A peripheral IV or heplock may be placed upon admission to the CRU and will be maintained according to site standards. The PIV/heplock will be removed prior to discharge.
- o. Confirm subject is using appropriate contraception methods per [Sections 4.4.3.2](#) and [4.4.3.3](#) for methods and duration.
- p. On Day 36 and Day 64 only the following tests from the chemistry panel are to be performed: ALT, AST, GGT, LDH, alkaline phosphatase, total bilirubin, direct bilirubin, indirect bilirubin and CK.
- q. Dosing window: The dosing windows for Day 29 or Day 57 may be extended to ± 2 days to allow for evaluation of ALT/AST if subject experiences $\geq 3 \times$ ULN, ALT or AST following the Day 1 dose. See [Section 3.3](#).
- r. Screening ADA sample collected only from subjects who participated in the SAD cohort and want to participate in the MAD portion as well.

TABLE OF CONTENTS

LIST OF TABLES	24
1. INTRODUCTION	25
1.1. Indication.....	25
1.2. Background	25
1.2.1. Non-Clinical Toxicology	26
1.3. Rationale.....	27
1.3.1. Study Rationale.....	27
1.3.2. Preliminary Unpublished Data (blinded).....	28
1.3.3. Dose Rationale.....	32
2. STUDY OBJECTIVES AND ENDPOINTS	34
2.1. Objectives.....	34
2.1.1. Primary Objective.....	34
2.1.2. Secondary Objectives	34
2.1.3. Exploratory Objectives	34
2.2. Endpoints.....	34
2.2.1. Primary Endpoints	34
2.2.2. Secondary Endpoints	34
2.2.3. Exploratory Endpoints	34
3. STUDY DESIGN.....	35
3.1. Study Overview	35
3.2. Planned Number of Subjects	37

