1.2. Background

Type 2 diabetes mellitus (T2DM) is a metabolic disorder afflicting over 25 million Americans and is growing rapidly in prevalence. Hyperglycemia is the primary clinical characteristic of T2DM, and is attributed to an underlying pathophysiology of insulin resistance, excess hepatic glucose production and deficient insulin production. Longstanding T2DM can lead to macro- and microvascular disease, resulting in a variety of complications, the most prevalent being cardiovascular disease, nephropathy, retinopathy and neuropathy. A number of large clinical outcome trials have demonstrated that improved glycemic control is associated with decreased microvascular complications ([Patel](#); [Turner](#)).

In addition to insulin, glucagon is a major hormone maintaining moment-to-moment glucose homeostasis. Glucagon counteracts glucose-lowering by insulin via the promotion of hepatic glucose production, thereby maintaining euglycemia and protecting against hypoglycemia. There is a growing appreciation for the potential role of glucagon in contributing to hyperglycemia in T2DM stemming from the observation that glucagon levels are inappropriately elevated in the T2DM hyperglycemic milieu ([Ali](#); [Dunning](#)). Therefore, mitigating the effects of hyperglucagonemia in T2DM is an attractive approach for treating hyperglycemia.

PF-06293620 is a humanized IgG2 Δ a monoclonal antibody that binds to, and blocks glucagon signaling through, the human glucagon receptor. Glucagon binding activates glucagon receptors found primarily on hepatocytes, leading to increased hepatic glucose production by a number of mechanisms including increased gluconeogenesis and glycogenolysis. PF-06293620 ameliorates elevations in plasma glucose, which are in part mediated by hyperglucagonemia, through normalization of dysregulated hepatic glucose production. Furthermore, as this mechanism is not dependent on functional pancreatic beta cells, it is anticipated to have a durable effect of improved glycemic control in subjects with T2DM.

CCI

PF-06293620

[figure not shown]
B3501001

Final Protocol Amendment 3 02 October 2015

CCI

CC1

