1.3.2. Preliminary Unpublished Data (blinded)

Subject Disposition and Baseline Characteristics (data-cutoff May 19, 2015)

Thirty-six subjects have been randomized, of which 12 have completed the study. To date, three subjects have discontinued from the study. One subject in Cohort 4 was no longer willing to participate and discontinued on Day 8; this subject was replaced with another subject. Two other subjects were no longer willing to participate in the study and were terminated early (1 each in the 1.0 mg/kg cohort and the 3.0 mg/kg cohort) and were not replaced.

The baseline characteristics of the subjects randomized to date in the SAD study are summarized in Table 1 below.

Table 1. Baseline Characteristics – SAD Cohorts, Study B3501001

Characteristics	Placebo N=9	Cohort 1 (0.3 mg/kg) N=6	Cohort 2 (1.0 mg/kg) N=6	Cohort 3 (3.0 mg/kg) N=6	Cohort 4 (6.0 mg/kg) N=9
Age ^{1,2}	57.1 ± 6.5	60.7 ± 4.5	60.7 ± 6.2	57.7 ± 4.5	57.4 ± 8.7
Gender ² (M:F)	4:5	5:1	2:4	3:3	5:4
Weight ^{1,2} (kg)	89 ± 21	93 ± 9	77 ± 14	90 ± 11	88 ± 16
BMI ^{1,2} (kg/m ²)	31.0 ± 4.6	32.3 ± 3.7	29.1 ± 3.3	30.8 ± 3.2	32.1 ± 3.4
Duration T2DM ³ (years)	10.9	13.4	10.0	8.5	8.1
Baseline HbA1c ^{1,4} (%)	8.7 ± 1.0	8.1 ± 0.9	7.7 ± 0.6	8.2 ± 0.5	8.3 ± 0.7

¹ Mean ± SD; Source; ² Table 14.1.2.1 (B3501001 IND Tables); ³ Table 14.1.2.2 (B3501001 IND Tables);

⁴ Table 14.4.7.5.1 (B3501001 IND Tables).

Pharmacokinetics (data-cutoff May 19, 2015)

As of May 19th 2015, preliminary, unpublished PK of PF-06293620 are available from the first 4 cohorts (0.3, 1, 3, and 6 mg/kg) in the ongoing single ascending dose study in subjects with T2DM. Following administration of single subcutaneous doses of PF-06293620, absorption was slow with median C_{max} occurring approximately 4-10 days post dose. After that the decline in concentration was slow and multiphasic with mean terminal half-life (t_{1/2}) ranging from 9 to 18 days as the doses increased from 0.3 to 3 mg/kg. Both C_{max} and total

exposure (AUC_{inf}) increased slightly greater than dose proportionally with increasing doses up to 6 mg/kg. Table 2 below summarizes the PF-06293620 preliminary, unpublished PK parameters.

Table 2. Geometric Mean (%CV) Plasma PF-06293620 Pharmacokinetic Parameter Values, Study B3501001 (Preliminary, unpublished, based on QCed data)

Parameter	PF-06293620 Treatment			
	0.3 mg/kg SC	1 mg/kg SC	3 mg/kg SC	6 mg/kg SC
N, n	6,2	6,5	6,6	6,0
AUC _{inf} (µg·hr/mL)	260	1748 (46)	6606 (45)	NC

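### Section 5.5 lists glucagon, unranked and without caution, as a hypoglycaemia rescue option although the study drug blocks the glucagon receptor

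*Protocol*

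**What the plan says.** Protocol Section 5.5 requires a blood sample for glucose first; the investigator "then may administer oral carbohydrate, glucagon or IV glucose according to medical judgment". The list has no order of preference and no warning. The section refers the reader to 7.6, which asks for a plasma glucose before treatment and has outpatients call the site, but adds no ranking or caution. Section 7.6.1 twice mentions subcutaneous glucagon, alongside food or carbohydrate and IV glucose, when defining a hypoglycaemic event and a severe one.

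The mechanism is in Section 1.2. PF-06293620 "binds to, and blocks glucagon signaling through, the human glucagon receptor", and on the physiology: "Glucagon binding activates glucagon receptors found primarily on hepatocytes, leading to increased hepatic glucose production".

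Section 1.3.2 gives preliminary single-dose SC pharmacokinetics: median peak concentration "occurring approximately 4-10 days post dose" and a mean terminal half-life "ranging from 9 to 18 days as the doses increased from 0.3 to 3 mg/kg".

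On blinding, Section 5.2 states: "Only the investigator site(s) and the study monitor(s) will be blinded to study treatment". On venous access in the MAD cohorts, footnote n of the MAD Schedule of Activities states: "A peripheral IV or heplock may be placed upon admission to the CRU".

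**The concern.** Of the three agents named in 5.5, glucagon is the only one that works through the receptor the study drug is designed to block. A member of staff following 5.5 as written could reasonably choose it, above all for a subject who is too impaired to swallow safely and has no line in place. Time could then be lost waiting for a response that the drug may have weakened. Section 7.6.1 foresees subjects who cannot treat themselves, and repeated low glucose values in one subject are a toxicity criterion in Table 7, so the protocol itself treats hypoglycaemia as a foreseeable event.

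The site cannot adapt its choice to the individual because it does not know who received active drug. A caution is useful only if it covers every dosed subject.

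**Working it through.** The claim is textual, and the plan gives no figure to reproduce. I set the sections side by side and then use simple arithmetic to show how long the question stays open.

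**1. Does 5.5 rank the agents or warn about glucagon?** No. Nor does 7.6, to which it refers, or 7.6.1. I found no such caution elsewhere in the protocol or SAP text available.

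**2. Does the protocol's own mechanism bear on the list?** Yes. Glucagon raises hepatic glucose through hepatocyte receptors, and the drug blocks signalling through that receptor (1.2). Oral carbohydrate and IV glucose supply glucose directly.

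**3. How large is the reduction?** Not stated. Section 1.3.3 indicates that blockade differs by dose: little or no pharmacological response is expected at 0.3 mg/kg, 75 mg every 4 weeks is placed near the half-maximal dose, and fasting glucose lowering appeared to level off by 3 mg/kg. The final MAD doses are 50, 75 and 150 mg (SAP Table 2).

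**4. How long does drug persist?** Inputs are the half-lives of 9 and 18 days (1.3.2), and the fraction left after t days is 0.5^(t / half-life).

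- One dosing interval, t = 28: 0.5^(28/9) = 0.116 and 0.5^(28/18) = 0.340, or about 12% to 34%.
- SAD Day 85, t = 84: 0.5^(84/9) = 0.0016 and 0.5^(84/18) = 0.039, or about 0.2% to 3.9%.
- MAD Day 169, t = 169 - 57 = 112 after the third dose: 0.5^(112/9) = 0.0002 and 0.5^(112/18) = 0.013, or at most about 1.3%.

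These fractions assume single-exponential decline and ignore absorption. Section 1.3.2 says "the decline in concentration was slow and multiphasic", so they are illustrative. They describe serum concentration, not receptor blockade, and do not measure harm. The half-life range stops at 3 mg/kg; no value for 6 mg/kg appears in the text available.

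**5. Where are subjects at peak concentration?** After a Day 1 dose the peak falls on about Day 1 + 4 = 5 to Day 1 + 10 = 11. SAD subjects leave the unit on Day 5. MAD subjects leave on Day 3 but are confined again on Days 6 to 8 (3.1), so part of that window is supervised.

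**6. How likely is the event?** No rate is given. Metformin is the only anti-diabetic therapy permitted close to entry. Recent severe hypoglycaemia or hypoglycaemia unawareness is excluded, as is screening fasting glucose below 60 mg/dL (4.2). Events needing non-oral rescue are probably few.

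**The case against.** The strongest reply is that 5.5 contains no wrong instruction. It is permissive, defers to medical judgment, follows a general requirement for standard supportive care, and already names two agents that bypass the receptor. Its readers are investigators whose protocol calls the drug a glucagon receptor antagonist. A caution may also exist in the blacked-out part of Section 1.2, in pages not available here or in the Investigator's Brochure. All of this stands as a limit on size. It does not remove the point: blinded staff treating an emergency have a list that names the opposed agent on equal terms, and a warning held elsewhere would not change what 5.5 tells them.

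Three stronger readings are tempting and are not supported:

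- *Glucagon would have little or no effect.* The documents give no measure of blunting, and the dose information in 1.3.3 indicates that blockade is not uniform. Reduced effectiveness is as far as they go.
- *IV glucose may be unavailable because lines are optional.* Footnote n concerns an indwelling line. Section 7.2.11 expects IV saline and IV epinephrine to be at hand, so sites are expected to be able to treat intravenously.
- *Hypoglycaemia counts or the stopping rule are compromised, because 7.6.1 partly relies on response to treatment.* That route applies only when glucose was not measured, whereas 5.5 requires a sample first. The hypoglycaemia criterion in Table 7 rests on a measured value below 40 mg/dL.

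**Conclusion.** The point holds as a safety wording issue confined to Section 5.5: glucagon is offered without ranking or caution in a trial of a glucagon receptor blocker. The expected consequence is a possible delay in effective treatment for a subject who cannot swallow and is given glucagon first. The size of the blunting and the number of such events are not stated; the events are probably few. No analysis, event definition or stopping rule is affected.

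The absence of a caution in the text supplied is certain. The reduced response is an inference from the stated mechanism, and its duration rests on preliminary half-lives at 0.3 to 3 mg/kg. A reader might infer that the protocol directs staff to use glucagon, or that affected subjects are all outside supervised care at peak exposure; the permissive wording of 5.5 and the MAD confinement on Days 6 to 8 show otherwise. The change should still be made, because it costs almost nothing and removes no option.

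**What to change.** Amend Section 5.5 to read, in substance: *For all dosed subjects (treatment is blinded), after the glucose sample give oral carbohydrate if the subject can swallow safely, otherwise IV glucose. Glucagon may be less effective because PF-06293620 blocks its receptor; use it only if IV glucose is not immediately available, and do not delay IV glucose to await a response.*

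Apply this from first dose through the end of each subject's follow-up and notify sites. Section 7.6.1 can stay unchanged, because it defines events and does not direct treatment.

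The cost is a few sentences and a site letter, with no new procedure, form or analysis. The caution also covers placebo subjects, in whom glucagon would work normally: by plan 5 x 2 = 10 of 40 in SAD (protocol Table 5) and 2 + 4 + 2 = 8 of 40 in MAD (SAP Table 2). They lose little, since the preferred agents are effective in them too. An amendment helps only subjects still in the study.
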